5.0 Procedures Involved

Our team will build, implement, and field test the TEAM strategy through a partnership between a large, multi-site FQHC (Access Community Health Network; 'ACCESS') in Chicago and Walgreens.

5.1 Performance Sites:

ACCESS. Access Community Health Network has been on the frontlines of community-based health care in Cook and DuPage counties for 25 years, serving the health needs of underserved communities by providing preventive care, chronic disease management, and other support services. In 2017, ACCESS served more than 183,000 individuals, including 26,117 patients with hypertension and 16,923 patients with diabetes. The patient population is low income and racially/ethnically diverse. ACCESS uses the **Epic EHR** platform (Verona, WI).

Walgreens Co. For 7+ years, our team has partnered with Walgreens on projects centered on innovations, medication therapy management (MTM), and partnerships with primary care. In 2018, [name] (MPI) coordinated a master research agreement between Northwestern and Walgreens. We are one of few academic partners formal collaborating with Walgreens through their Center for

STU#: STU00209066

Health and Wellbeing Research. With >8,000 stores in the US (heavily populated in medically underserved areas), Walgreens ranks as the largest retail community pharmacy chain.

The following five ACCESS Health Centers have collocated Walgreens community pharmacies and current read-only access for Walgreens pharmacists in place:

1. ACCESS Grand Boulevard
2. ACCESS Genesis
3. ACCESS Hawthorne
4. ACCESS La Villita
5. ACCESS Madison

The TEAM intervention will be rolled out initially at the Hawthorne and Genesis sites. If needed, the pilot will be rolled out at the Grand Boulevard, La Villita, and/or Madison site. The intervention will be rolled out as follows: Walgreens pharmacists will be notified of the enrollment of a patient in the intervention by the Walgreens Research Analytics Team. Each pharmacist will conduct 2-3 CMRs a week at these locations. For this pilot, we will be using trained community pharmacists and possibly community pharmacist residents.

5.2 Phases of the Project

The following activities will be performed during the proposed project, by phase:

Design Phase (months 1-9)

1. Organize Northwestern-Walgreens-ACCESS team; establish project milestones, roles.
2. Convene all stakeholders (primary care providers, Walgreens pharmacists and leadership) to gather feedback on the initial draft standard operating protocol (SOP) for the implementation of TEAM in ACCESS clinics, leveraging Walgreens pharmacists will be developed. This is an iterative process with all TEAM users.
3. Amend existing Walgreens-ACCESS agreements to include new Epic read/write access, given the parameters established by the mutually-agreed upon SOP. This includes the specification of set security points within the ACCESS EHR (Epic) that both allows and controls pharmacist permissions. Our Northwestern team has already worked with ACCESS and Walgreens to detail the TEAM protocol (see section 4.0 study intervention).
4. Devise an implementation evaluation battery capturing process outcomes and also a range of patient-reported medication safety-related outcomes.

Implementation phase (months 10-30)

5. 'Beta test' the TEAM strategy in the clinical environment to confirm the functionality of all bi-directional information sharing components.
6. Trouble shoot any technical/procedural concerns, modifying the SOP accordingly.
7. Orient participating ACCESS clinical sites and Walgreens staff on the final SOP in preparation for the live implementation to be conducted in the second project phase.
8. Implement the finalized TEAM intervention protocol defined in the Design Phase at ACCESS clinic sites. The strategy includes Walgreens pharmacist outreach with identified

STU#: STU00209066

ACCESS patients to: a) perform medication reviews, b) generate automatic and tailored EHR-based alerts; c) provide clinical decision support.

9. Enroll 120 patients into the pilot study.
10. Randomize patients (1:1) to either: 1) the TEAM intervention or 2) enhanced usual care.
11. Conduct baseline (by phone) and 2 month follow-up interview (by phone) with enrolled patients. Interviews will include validated measures and will be completed using RedCAP software for data quality and safety. Data will also be abstracted from patient EHR records at 12 months post-enrollment.

Evaluation Phase (months 31-36)

12. At the completion of the Implementation Phase, conduct structured telephone or in-person interviews (as appropriate) with Walgreens pharmacists and its leadership who were involved in the TEAM project to capture their project-specific experiences, perceptions of benefits, challenges, and other constructive feedback leading to necessary modifications.
13. Collect and merge all pertinent data sources (EHR), Walgreens, pharmacy records, patient report (qualitative and quantitative), perform quality assurance activities in preparation for formal analyses.
14. Conduct details analyses in response to Aims 1-3.
15. Share preliminary analyses with ACCESS, Walgreens and study team.

5.3 Study Arms

Enhanced Usual Care. Patients randomized to enhanced usual care will have the medical record available to a Walgreens pharmacist with 'read only' access. All patients at the five targeted health centers already have read-only access in place. This means the Walgreens pharmacist will have the capability to review an ACCESS patient's record as necessary. 'Read only' permissions are becoming more commonplace with increased adoption and linkage of health information technologies between healthcare organizations. While this health information exchange presents opportunity for a pharmacist to engage patients in a more informed manner for MTM, existing pharmacy practice workflows will remain unchanged. Pharmacists will not have dedicated effort to perform MTM. While they are not prevented from proactively engaging with patients to perform medication reviews or contacting ACCESS prescribers to share information, it is a rare occurrence due to workflow. At present, the pharmacist may refer to the EHR as needed and in a reactive manner; such as if a patient were to request a medication requiring review for billing purposes (i.e. verify insurance, prior authorizations), or if a patient safety concern was raised (e.g. potential drug-drug or drug- disease interaction, therapeutic duplication, etc.). Similarly, read only EHR access means pharmacists must continue to use existing communication channels (e.g. phone, fax) to contact prescribers. These channels can be onerous and inefficient.

Intervention: TEAM strategy. See section 4.0 Study Intervention.

5.4 Randomization & Blinding.

Patient-level randomization will occur within ACCESS health centers. At each site, participants will be randomized via a 1:1 scheme to intervention or 'enhanced usual care' (N=120; n=60 per

STU#: STU00209066

arm) in randomized block sizes of 4 or 6 using SAS PROC PLAN. We will blind personnel involved in statistical analyses ([name], [name]) and also the principal investigators ([name], [name]) and coinvestigators. Site project managers and RCs will have access to study arm assignments to initiate TEAM components to those randomized to receive them.

Limitations to Randomization Scheme. As a 'diffuse' intervention that addresses patients and the health system (ACCESS), we recognize prescribers at ACCESS sites will be caring for patients in both study arms of our trial. While there may be risk of potential contamination, our extensive experience working in time-constrained, resource-limited FQHC practices would suggest this to be of minimal concern. Other randomization options, either by clinic or by prescriber, are more problematic. FQHC practice sites are heterogeneous, and also have prescribing clinicians that work across sites. Our team strongly felt that patient-level randomization, wherein we could also control the receipt or withholding of TEAM services under study, was the most formidable, pragmatic approach.

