We will ask patients (yes/no) whether their prescriber/nurse/pharmacist counseled them about their medications. We will also ask the Health Literacy supplemental items of the Consumer Assessment of Health Providers Survey (CAHPS) to evaluate the extent and quality of provider verbal counseling on Rx medications.

For the outcomes described below, we only include chronic Rx medications. Though we document them, we exclude PRN or limited duration drugs, as adherence concerns are different. All of these measures have been used in multiple studies by our team; results have been published extensively.

Medication Reconciliation

At each interview, commissions (medications listed in the EHR and the patient reported not taking) and omissions (patient reported medications not in the EHR) will be calculated based on medication lists and patient self-report.

Medication knowledge. Medication-specific knowledge will be measured through a series of open-ended questions, capturing patients' knowledge of each of their medication's: 1) indication for use and 2) risks, warnings or potential side effects. Answers will be qualitatively reviewed and independently scored as correct/incorrect by two RCs according to medication information provided from ACCESS and Walgreens. For any that the RCs do not have information on or any with discordance between RCs, a pharmacist will qualitatively review and independently score as correct/incorrect.

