Medication dosing errors. We will use a 24-hour recall procedure utilized extensively by this team in prior and current studies to assess Rx dosing errors. At each interview, RCs will review medications reported as taken by the patient and those listed in the EHR to create a final list of medications prescribed to the patient. RCs will then ask patients to report, one by one, how they took each medication over the past 24 hours. Patients will be asked to specify the amount taken (i.e. dose) and when taken (to determine frequency and interval between doses). Patients will be asked to report whether this was how the medication was prescribed, and if not, will be queried: 1) to determine the reason for not taking the medication as prescribed (i.e. forgetfulness, ran out of medication) and 2) to describe how the medication *should* be taken. Data from this exercise will be used to assess correct dosing (yes/no) based upon the instructions for each medication. It will also be used to calculate regimen consolidation, or the total number of time points throughout the 24-hour period that a patient reported taking one or more medicines (count variable, range: 1-24).

Medication adherence. Adherence will be measured using: 1) the Ask-12 survey and 2) the proportion of days covered (PDC) according to pharmacy records. The Ask-12 is a brief measure of adherence that covers three domains: inconvenience/forgetfulness, treatment beliefs and behavior. In prior studies, the tool demonstrated good internal consistency reliability (Cronbach's α 0.75) and test-retest reliability (intraclass correlation 0.79); convergent validity was also

STU#: STU00209066

demonstrated through correlations with multiple other measures (Morisky, SF-12) and pharmacy claims data. Ask-12 scores range from 12-60, with higher scores indicating poorer adherence. PDC will be calculated by summing the number of days' supply obtained by a patient during a given time period and dividing by the number of days for which the medication was prescribed. For each patient, we will assess adherence within drug class. If a patient fills a prescription for a drug and switches to another drug within the same class, all prescriptions will be summed in the numerator. Adherence will be treated continuously and dichotomously (yes/no; PDC at disease-specific threshold based on Pharmacy Quality Alliance (PQA) standards). PDC data will be automatically obtained from Walgreens as part of the TEAM study.

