Training will begin after questionnaire and interview protocols have been refined and standardized. The PIs and project manager will lead sessions to orient the research staff to the surveys and study protocols (e.g., interview process, use of laptop PCs, data security). All interviewers will be required to demonstrate competence in survey administration. All interviews will be conducted via REDCap, a secure, web-based application. Recruitment outcomes along with identifiable data necessary to contact participants will be recorded in NU's REDCap. Interviews will be conducted by research coordinators (RCs) over the phone. RCs will read each question aloud and record patient

STU#: STU00209066

responses directly onto a password protected laptop or PC computer using REDCap. Study interview data does not contain any identifiable information, and are identified by project staff by an assigned study ID. All identifiable information will remain in the secure REDCap system. Contacts with enrolled participants will be made via email, USPS and telephone.

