Each subject will be tracked using an Access database. The database, containing identifiers and other related information for coordinating research activities (recruitment outcome, interview call log and interview visit schedule, etc.) will be kept on the secure Northwestern network drive. Only the PI, project manager, and RC will have access to this database. ACCESS participants will be additionally tracked in their EPIC EMR system, only accessible by ACCESS study personnel.

Data will be collected via REDCap. REDCap is a secure, encrypted online data collection tool, which can only be accessed by NU authorized personnel listed on the project's IRB.

Several methods will be employed to reduce the risk of breach of confidentiality. A study identification number will be assigned to each subject in the study. The research data collected and stored will have the study identification number and no other identifying information on it. The de-identified study data will be kept in a separate locked file cabinet. Using this method, if someone were to gain illegal access to the locked filing cabinet with study data, they would have no way to link this data to any identifying information.

17.3 Quality Assurance.

Training will begin after surveys and interview protocols have been refined and standardized. A training session will be conducted by Drs. [name] and [name]. The training will include tailored discussion of 1) roles and responsibilities; 2) HIPAA and IRB mandates (completion of Human Subjects Training Program - CITI; 3) effective recruitment communication and interviewing with attention paid to health literacy and culture; and 4) gathering and recording data including administering the structured survey electronically. Role playing will be used to fine tune training for obtaining informed consent and interviewing patients. Institutional Review Board (IRB) approval will be attained at both sites prior to any active recruitment efforts. All interviewers will be required to demonstrate competence in survey administration.

STU#: STU00209066

17.4 Study-wide data management.

Data collected includes patient consent forms, data gathered using the ACCESS patient lists, and data collected during the study interviews.

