Data Access. The Data Custodian is the Principal Investigator, [name]. Only authorized personnel listed on each institutions IRB will have access to the data. Any information that could allow identification of individual participants, including the master list, will be kept strictly confidential.

Local Data Storage. Data will be stored in REDCap, a secure, web-based application, and on the Northwestern secure server for the length of the study. The Project Manager or Data Analyst will download the de-identified data only from REDCap monthly and save to the “Analytic” folder within the TEAM project folder on the FSM department servers which are located in a HIPAA compliant data center. These data files do not contain any identifiable information, and are identified by project staff by an assigned study ID. All identifiable information for ACCESS patients will remain in the secure REDCap system. Upon completion of all study activities, a final de-identified dataset will be created and all identifiable information will be deleted. This dataset will be stored indefinitely on the GIM server for secondary analyses. Only authorized personnel will have access to the dataset. All identifiable information will be deleted upon completion of the study

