19.0 Provisions to Protect the Privacy Interests of Participants

19.1 Information about study subjects will be kept confidential and managed according to the requirements of the Health Insurance Portability and Accountability Act of 1996 (HIPAA). In order to preserve participants’ confidentiality rights, research subjects will be assigned code numbers that will be used to identify all the information collected. Using these codes, none of the collection forms will contain the names of the participants. All electronic data will be stored in on a password-protected computer. A Microsoft Access master study tracking database will contain information linking participants to their study id numbers. This database will be encrypted and kept on a secure server and only accessible by study personnel.

19.2 Survey data will be stored in a REDCap. Individual study identification numbers will be assigned to each participant and only this number will appear on the survey. Subjects will be told that unless required by law, only the study investigators, members of the project staff, the funding agency and representatives of Institutional Review Boards will have the authority to review any study records. In such cases, these parties too will be required to maintain confidentiality. The final data set will be stripped of identifiers. Data will be shared via presentations at national and international meetings and in peer reviewed publications. Furthermore, all results will be shared with the funding institute.

STU#: STU00209066

19.3 Participation in the study poses minimal risk of psychological, social and economic harm. Informing subjects in advance that they may decline to answer any questions asked during the interview will mitigate any risks associated with expressing their opinions (e.g., feeling uncomfortable).

19.4 All enrolled participants will provide e-consent, include HIPAA authorization for the collection of all data, including review of the patient's medical record. For those who are unable to provide e-consent due to inability to access the required technology, they will undergo verbal consent with an alteration of HIPAA Authorization, as described below in sections 22.0 and 24.0.

19.5 Only authorized personnel listed on each institutions IRB and approved by the PI will have access to the data.

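### Research coordinators, as a role, hold arm assignments and also score the open-ended medication-knowledge answers; the plan masks neither these scorers nor the adjudicating pharmacist

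*Combined protocol and SAP*

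**What the plan says.** Section 5.4 (Randomization & Blinding) names who is blinded: the statistical personnel, the principal investigators and the coinvestigators. It then says that "Site project managers and RCs will have access to study arm assignments to initiate TEAM components to those randomized to receive them". No RC group is described as masked.

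Section 5.5, under Medication knowledge, asks patients open-ended questions about the indication and the risks of each medicine. "Answers will be qualitatively reviewed and independently scored as correct/incorrect by two RCs", using medication information supplied by the two partner organisations. "For any that the RCs do not have information on or any with discordance between RCs, a pharmacist will qualitatively review" and score the answer.

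Section 12.2 adds that "Interviews will be conducted by research coordinators (RCs) over the phone", and its recruitment text links the Northwestern RC to the step that randomises the patient. Interview data are stored under a study ID. On the participant tracking database, section 17.2 says "Only the PI, project manager, and RC will have access to this database", and section 19.1 says "A Microsoft Access master study tracking database will contain information linking participants to their study id numbers".

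**The concern.** Medication knowledge is listed among the effectiveness outcomes, and it is the one whose scoring the plan itself describes as a qualitative review. Whether a free-text answer about a side effect is good enough is a judgement. If the person judging knows, or can readily find out, that the patient had a pharmacist review, borderline answers may be credited more often in the TEAM arm. Such a lean goes straight into the arm contrast, and blinding the analysts cannot remove it because it is already in the recorded values.

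The reason given for RC access to assignments is to start TEAM components. Scoring recorded answers does not need that access. Patients and the pharmacists who deliver TEAM cannot be masked, but the scoring can be.

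**Working it through.** **Reading the passages together.**

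1. Arm knowledge: section 5.4 gives it to RCs as a role.
2. Scoring: section 5.5 gives it to two RCs. That they score independently means separately; it says nothing about masking.
3. Adjudication: a pharmacist sees only answers that are discordant or that the RCs have no information on. An answer that both RCs wrongly credit is concordant and goes no further. The plan does not say whether this pharmacist is masked or is one of the pharmacists who deliver TEAM.
4. Study IDs: RCs can open the tracking database (17.2), which links IDs to participants (19.1), and the RC role also holds assignments (5.4). The coding protects confidentiality but does not mask the arm.

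**Size, as illustration only.** The plan gives no scoring error rate, agreement figure, expected proportion correct or power calculation, so it has no figure to reproduce.

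Inputs:
- n = 60 per arm (section 5.4).
- Assumed: m = 5 scored answers per patient, one per medicine; p = 50% truly correct in both arms; within-patient correlation ρ = 0.1, 0.3 or 0.5; two-sided 5% test.
- Assumed: a shared lean of d points, in the TEAM arm only.

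Share of wrong TEAM answers that must be credited = d/(1 − p):
- 1 point: 0.01/0.50 = 2%
- 2 points: 0.02/0.50 = 4%
- 5 points: 0.05/0.50 = 10%

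Simulation: 20,000 trials per cell, beta-binomial patients, no true difference, t test on patient-level proportions. This approximates the two-level model in section 17.1.

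| Lean | ρ = 0.1 | ρ = 0.3 | ρ = 0.5 |
|---|---|---|---|
| 0 points | .052 | .048 | .050 |
| 1 point | .056 | .056 | .053 |
| 2 points | .071 | .063 | .060 |
| 3 points | .097 | .079 | .074 |
| 5 points | .175 | .131 | .110 |

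Closed-form check of the 5-point row. The variance of a patient's proportion is p(1 − p)[1 + (m − 1)ρ]/m = 0.25(1 + 4ρ)/5 = 0.070, 0.110, 0.150. The standard error of the difference is √(2 × variance/60) = 0.0483, 0.0606, 0.0707. Then z = 0.05/SE = 1.035, 0.826, 0.707, and Φ(z − 1.96) + Φ(−z − 1.96) = .179, .131, .109, in agreement with the simulation.

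Sensitivity:
- With 48 per arm followed up (assumed), the simulated 5-point row is .154/.118/.099.
- Over 3, 5 or 8 medicines and 50% or 70% correct, at 60 per arm, the ranges are .050-.060 (1 point), .058-.082 (2 points) and .105-.272 (5 points).
- Section 5.5 scores two items per medicine. Taking m = 10 answers with the same ρ throughout, the closed form gives .241/.147/.114 at 5 points.

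If the two RCs erred independently, each would have to mis-credit √0.10 = 32% of wrong TEAM answers to produce 5 points. The 5-point row therefore presumes a shared lean or a leaning adjudicator.

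**The case against.** The best case for the plan has four parts.

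**Only site RCs may be unblinded.** The word Site in section 5.4 could govern RCs as well as project managers, and section 12.2 distinguishes ACCESS RCs from Northwestern RCs. This does not hold up well, because section 12.2 ties the Northwestern RC to randomisation and no masked RC group is defined anywhere.

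**The tracking database is not said to hold the arm.** This is correct; the blinded principal investigator has access to the same database. It takes a scorer from ID to patient, and the arm must come from elsewhere. Section 5.4 gives the RC role that other source, but a scorer working on coded answers is not shown to see the arm while scoring.

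**The weight is limited.** This is a 120-patient pilot with many outcomes. Knowledge is not one of the three targets named in Aim 1, though it bears on safe use. Refill-based adherence and abstracted clinical markers do not depend on this scoring. All of that stands.

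**Scoring is done twice against reference information.** This limits random error and independent mistakes, but not a lean in common.

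A reader might infer that the RCs who know the arm are the very people who score, or that the adjudicator is a TEAM pharmacist. The documents name roles, not individuals, and are silent on the pharmacist's identity; neither inference is shown. The text between sections 24 and 25.2 was not available, so role separation described there cannot be excluded.

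**Conclusion.** The gap is real: in the text available, a role that holds assignments also scores an outcome requiring judgement, with no masking of the scorers or the adjudicator and no separation of duties. Its effect is unknown. Under the assumed inputs, a shared lean of 1-2 points is negligible (about 5-7% false positives), and one of 5 points gives roughly 11-18%; the second figure requires a tenth of wrong TEAM answers to be credited in that arm alone.

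It is tempting to take much larger leans and conclude that a positive knowledge result could not be trusted. The documents give no basis for a lean of any size, so that conclusion is not supported. Nor does the point extend to dosing errors as written: "Data from this exercise will be used to assess correct dosing (yes/no) based upon the instructions for each medication" names no scorer and describes a comparison that needs less judgement.

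This should be corrected because the better method costs little. It does not invalidate the pilot.

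**What to change.** In sections 5.4 and 5.5, state that:
- knowledge answers are scored from an extract without arm;
- the extract uses recoded IDs that scorers cannot link to the tracking database or to the assignments;
- baseline and follow-up answers are mixed, and any mention of the pharmacist call is redacted;
- the adjudicating pharmacist is masked and does not deliver TEAM.

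If masked scorers are already intended, a sentence naming the separation of roles would cover most of this. Report self-reported outcomes as unmasked.

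Cost: no added patients, visits or measures. Section 17.4 already provides a base for the extract: "The Project Manager or Data Analyst will download the de-identified data only from REDCap monthly". The extra work is redacting English and Spanish free text, having someone other than the scorers hold the recode key, and scoring in batches instead of after each call.

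Limits: an RC may still recognise an answer from an interview that RC conducted. Masked scoring also does nothing about an unmasked interviewer's probing or transcription, or about patients' own reporting.

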At the end of the week, the ACCESS RC will send a list of patients that agreed to be contacted to Northwestern. The Northwestern RC will then screen the patient to determine eligibility (English or Spanish-speaking, responsible for administering medication regimen, taking 5+ medications, prescribed at least one medication from any of the selected six therapeutic classes (confirmed via brief chart review), no severe cognitive, hearing, visual impairment). If eligible, the RC will obtain informed online or verbal consent at the end of the call. If the patient is unable to stay on the phone to consent, the RC will schedule a follow up call to consent the patient before the baseline will be done. During the screening and consent call, the Northwestern RC will schedule the call to conduct the baseline assessment and randomize the patient to study arm. Prior to the baseline interview, the Northwestern RC will conduct a more thorough review of the patient medication list through either receiving a file from ACCESS or through read ability in EPIC for patient charts.

Recruitment Letters

An ACCESS RC will mail a letter to patients remaining on the list, notifying them that a RC from Northwestern University will be phoning to invite them to participate in a study. Patients will have the opportunity to opt out of being contacted. Ten days after the mailing, the Northwestern RC will start to contact patients by phone to ask if they would be interested in participating. If interested, the RC will screen the patient to determine eligibility (English or Spanish-speaking, responsible for administering medication regimen, taking 5+ medications, prescribed at least one medication from any of the selected six therapeutic classes (confirmed via brief chart review), no severe cognitive, hearing, visual impairment). If eligible, the RC will obtain informed online or verbal consent at the end of the call. If the patient is unable to stay on the phone to consent, the RC will schedule a follow up call to consent the patient before the baseline will be done. During the screening and consent call, the Northwestern RC will schedule a phone interview to conduct the baseline assessment and randomize the patient to study arm. Prior to the baseline interview, the Northwestern RC will conduct a more thorough review of the patient medication list through either receiving a file from ACCESS or through read ability in EPIC for patient charts.

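### Sections 5.4 and 12.2 do not conceal allocation: the coordinators who screen, consent and randomise may also see arm assignments in small within-site blocks, so the next arm could be guessed at most about 69% of the time

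*Combined protocol and SAP*

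**What the plan says.** Section 5.4 sets out the scheme: "Patient-level randomization will occur within ACCESS health centers", and "At each site, participants will be randomized via a 1:1 scheme to intervention" or enhanced usual care, "in randomized block sizes of 4 or 6 using SAS PROC PLAN". Analysts, principal investigators and coinvestigators are blinded. Two groups are not: "Site project managers and RCs will have access to study arm assignments to initiate TEAM components to those randomized to receive them".

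Section 12.2 describes enrolment. In the telephone route, "The Northwestern RC will then screen the patient to determine eligibility". Then "If eligible, the RC will obtain informed online or verbal consent at the end of the call". On that same call "the Northwestern RC will schedule the call to conduct the baseline assessment and randomize the patient to study arm". The letter route gives the Northwestern RC the same steps.

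The plan does not say who holds the allocation list, what event releases an assignment, or that RCs who recruit are different people from RCs who see arms. The only limitation that section 5.4 discusses for the scheme is contamination through shared prescribers.

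**The concern.** Whoever decides whether a patient enters the trial should not be able to foresee that patient's arm. Here one role does the screening, consenting and randomising, and the same role title appears among those with access to assignments. The blocks are small and run within site, and the trial starts at two sites. Anyone who tracks earlier assignments at a site can name the arm that is behind and be right more often than chance.

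The RC has some room to act on such a guess: effort put into the consent conversation, when the baseline call is booked, and the vision and hearing exclusions, for which section 9.2 gives no cut-offs. Aim 1 is a between-arm efficacy comparison that rests on randomisation. Most of its outcomes come from patient interviews and may depend on engagement, which an RC can sense on the telephone.

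The issue is foreknowledge of the arm at enrolment. Knowledge of the arm at the follow-up interview is a separate matter.

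**Working it through.** The documents give no predictability figure and no power calculation, so there is no figure of theirs to reproduce.

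**Inputs.** From section 5.4: 1:1 allocation within site, and blocks of 4 or 6. From sections 5.2 and 5.4: 120 patients, 60 per arm. From section 5.1: two sites at first, up to five. The mix of block sizes is not stated; I assume each is equally likely and show the range.

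**Guessing rate with full knowledge.** The rule is to guess the arm that is behind at the site and to toss a coin when the arms are level. In a block of 2m, the expected number of correct guesses is m + (4^m / C(2m,m) − 1)/2.

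- Block of 4 (m = 2): 2 + (16/6 − 1)/2 = 2.833 of 4 = 70.8%.
- Block of 6 (m = 3): 3 + (64/20 − 1)/2 = 4.1 of 6 = 68.3%.
- Equal mix: (2.833 + 4.1)/10 = 69.3%, about 83 of 120 against 60 by chance.

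Any mix lies between 68.3% and 70.8%. Full enumeration of the blocks agrees. Simulation with a truncated last block gives 69.1% (two sites of 60) and 68.7% (five sites of 24). Varying the block size does not prevent this, because the running imbalance returns to zero at the end of every block, whatever its length.

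**When the guess is made earlier or on partial knowledge (simulated).**

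| Situation | Correct guesses |
|---|---|
| 1 other site patient randomised in between | 59% |
| 2 in between | 55–56% |
| 3 in between | 52% |
| RC sees a random half of earlier assignments | 54–56% |

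**Bias.** Let p be the guessing rate, and d the difference in expected prognosis between patients enrolled when TEAM is guessed and those enrolled when control is guessed. The TEAM arm contains a share p of the first kind and the control arm a share 1 − p, so the arms differ by (2p − 1)d. The documents give no value for d; 0.1 to 0.3 SD is an assumption for illustration.

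- p = 0.693: 0.387d, or 0.04 to 0.12 SD.
- p = 0.59: 0.18d, or 0.018 to 0.054 SD.
- p = 0.52: 0.04d, or 0.004 to 0.012 SD.

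**Would the planned adjustment catch it?** Section 17.1 adjusts for baseline variables that differ at p < .05. With 60 per arm, the standard error of a difference in SD units is √(2/60) = 0.183. A true imbalance of 0.04 to 0.12 SD is then 0.2 to 0.6 standard errors and reaches p < .05 only about 5 to 10% of the time.

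**Would larger blocks help?** A block of 8 gives 4 + (256/70 − 1)/2 = 5.329 of 8. An equal mix of 4, 6 and 8 gives (2.833 + 4.1 + 5.329)/18 = 68.1%, which is hardly lower.

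**The case against.** The strongest reply is that 69% is a ceiling. It needs an RC who knows every earlier assignment at the site, keeps a tally, and has the next patient randomised there. Section 12.2 can be read as placing randomisation at the later baseline call, and consent itself may move to a follow-up call. That stands, and it is why the lower rates belong beside the ceiling. It does not bring the rate to chance. Section 8.0 plans a 20-month enrolment window: 120/20 = 6 patients a month, or about 3 per site per month at two sites, so a short gap will often contain no other patient. The pace of 2–3 medication reviews per pharmacist per week in section 5.1 would allow faster enrolment and lower predictability.

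Discretion is also limited. Most eligibility criteria come from the EHR data pull (section 9.1), physicians can remove patients (section 12.1), an ACCESS RC makes first contact in the telephone route, and cognition is measured with a named screener. That stands too. What remains is consent effort, scheduling, and vision and hearing.

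The plan does not say whether ACCESS RCs, Northwestern RCs or both see the arms. True, but it has the Northwestern RC randomise and states no separation.

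Finally, RCs who conduct follow-up interviews may learn arms anyway. That happens about two months after baseline, when at 3 patients per site per month some 6 more have been randomised and the block in question has usually closed.

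**Conclusion.** The point holds as a gap in allocation concealment. As written, the plan lets the enrolling role predict the next arm at most about 69% of the time (68–71% over any block mix) given full knowledge and no gap, and about 52–59% with one to three intervening patients. Under the assumed d, the bias is at most 0.04 to 0.12 SD, or about 0.004 to 0.054 SD at the lower rates. The planned covariate screen would not reliably catch it, and it cannot reach unmeasured motivation.

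A reader might infer more than the documents support:

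- That the next arm is simply known. This would follow only if access covers the future list. The text does not settle this, and the stated purpose of starting TEAM for patients already randomised points to past assignments.
- That bias will occur. The documents show an opportunity only.
- That nearly all outcomes are self-reported. Proportion of days covered comes from pharmacy records, and HbA1c, LDL cholesterol and blood pressure are abstracted (section 5.5).
- That no analysis could help. Section 17.1 does adjust for some measured imbalances; the claim here is only that it is unreliable for this purpose.

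**What to change.** State in sections 5.4 and 12.2 that:

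- the PROC PLAN list is loaded into the REDCap randomisation module (REDCap is already the data collection system);
- each arm is released only after eligibility, consent and the baseline interview are recorded, which also settles when randomisation happens;
- recruiting RCs cannot see the list or cumulative assignments, so the released arm goes to the site project manager; an RC shown each arm in turn could rebuild the tally;
- the site project manager sends Walgreens the weekly list of TEAM patients that section 4.2 requires.

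An RC who cannot see earlier assignments guesses at 50%. Hiding the block sizes or adding larger blocks is not worth pursuing: the guess needs only the running imbalance, and adding blocks of 8 leaves the rate at 68.1%.

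The cost is a one-off set-up, wording changes in two sections, and moving the TEAM referral trigger from the RC to the project manager. A small residual remains if the same RC recruits and follows up at a slow site. At five sites with even enrolment, 6/5 = 1.2 patients per site per month gives about 2.4 in two months, and the rates for 2 to 3 intervening patients (about 52–55%) would apply.
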